The pharmacologic actions of isoprenaline appear to be terminated principally by tissue uptake. The drug is metabolized by conjugation in the GI tract and by the enzyme catechol-*O*-methyltransferase in the liver, lungs, and other tissue. The major metabolite after IV administration is 3-*O*-methylisoproterenol (which has been reported to have weak β -adrenergic blocking activity) and its conjugates. The duration of action is brief(2).

In America, Isoprenaline (in the hydrochloride form) has been licenced under the trade name Isuprel[™] by the Food and Drug Administration (the FDA) for use since 1956. Licensed routes of administration of Isuprel[™] include central or peripheral intravenous administration as an infusion or bolus injection, intramuscular, subcutaneous or intracardiac routes. As an infusion, recommended

dosing ranges are between 0.5mcg/min to 30mcg/min. The drug should be stored at between 20 and 25°C(3).

Licensed indications include;

- For mild or transient episodes of heart block that do not require electric shock or pacemaker therapy.
- For serious episodes of heart block and Adams-Stokes attacks (except when caused by ventricular tachycardia or fibrillation)
- For use in cardiac arrest until electric shock or pacemaker therapy, the treatments of choice, are available.
- For bronchospasm occurring during anaesthesia.
- As an adjunct to fluid and electrolyte replacement therapy and the use of other drugs and procedures in the treatment of hypovolemic and septic shock, low cardiac output (hypoperfusion) states, congestive heart failure and cardiogenic shock.

Although unlicensed in the UK, Isoprenaline is extensively used. Its indications in modern practice include its use for patients presenting to hospital with abnormal, slow heart rhythms and as an infusion to provide physiological stress to the heart for diagnostic scans. Most commonly, Isoprenaline is used in the cardiac electrophysiology laboratory as part of routine clinical electrophysiology studies to diagnose abnormal heart rhythms with a view to abolishing them using an ablation technique. It is used in this setting numerous times every day in every centre in the UK with specialist electrophysiology services. It is considered a standard part of the procedure and is used in combination with programmed electronic stimulation to induce arrhythmias that they might be categorised and treated(4).

Background

Atrial Fibrillation

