 - Alternative hypothesis is that there is significant difference in the proportion of subjects who experience the occurrence of an episode of atrial fibrillation during the infusion protocol when comparing those who receive the isoprenaline infusion with those who receive the placebo infusion.

- Double blinded. Event rate in Isoprenaline group likely >30%. Event rate in placebo group likely <5%. For 90% power and 95% significance projected to need 31 participants per group.
- For higher event rates, fewer participants required. 15 participants per group for event rate >50%, 6 participants per group for event rate >80%.
- Aim to recruit 30 participants per group.

Experiment 3

- Does an infusion of the drug Isoprenaline induce Atrial Fibrillation in subjects following an ablation procedure for common type atrial flutter?
 - Null hypothesis under investigation is that there is no significant difference in the proportion of subjects who experience the occurrence of an episode of atrial fibrillation during the infusion protocol when comparing those who receive the isoprenaline infusion with those who receive the placebo infusion.
 - Alternative hypothesis is that there is significant difference in the proportion of subjects who experience the occurrence of an episode of atrial fibrillation during the infusion protocol when comparing those who receive the isoprenaline infusion with those who receive the placebo infusion.
 - Double blinded. Event rate in Isoprenaline group likely >30%. Event rate in placebo group likely <5%. For 90% power and 95% significance projected to need 31 participants per group.
 - Aim to recruit 35 participants per group.

Experiment 4

- Does an infusion of the drug Isoprenaline induce Atrial Fibrillation in subjects following an ablation procedure for either Atrio-Ventricular Re-entrant Tachycardia (AVRT) or Atrio-Ventricular Nodal Re-entrant Tachycardia (AVNRT)?
 - Null hypothesis under investigation is that there is no significant difference in the proportion of subjects who experience the occurrence of an episode of atrial fibrillation during the infusion protocol when comparing those who receive the isoprenaline infusion with those who receive the placebo infusion.

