This protocol will also collect data regarding the inducibility of atrial fibrillation by an isoprenaline infusion in participants prior to atrial flutter and SVT ablation and after a pulmonary vein isolation procedure. In the pulmonary vein isolation group this will allow analysis of the change in inducibility associated with that procedure. These data will be reported as secondary, hypothesis generating experimental analyses and hence are not associated with detailed power calculations as in the defined analyses above.

Study Design

This project investigates different aspects of the use of isoprenaline to induce an occurrence of atrial fibrillation through a number of different experiments. Data from any one participant may be used in a number of the experimental analyses, however participation in the study will follow one of 2 schedules for any given subject. As this is the case the project has been presented in two parts, with participants in Part A sharing a similar experience which will be different to those participating in Part B and vice versa.

Of note, where eligible, subjects will be offered the opportunity to participate in more than one part of the study. For example, a participant with a diagnosis of paroxysmal atrial fibrillation could take part in Protocol Part A and then go forward for an ablation procedure, associated with which they could take part in Protocol Part B. To avoid possible contamination of results, this will not be allowed where it will mean that study drug infusions for different parts of the study will occur closer than 2 weeks apart.

Protocol Part A

This part of the project investigates the consistency of the outcome of repeated administrations of an isoprenaline infusion. Subjects for this part will be recruited independent of their need for an ablation procedure. The isoprenaline, study drug infusion is administered on an open label basis on two separate occasions at least 2 weeks apart. Administration will be in a ward based environment. No follow up visits will be required.

Protocol Part B

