- Ongoing angina symptoms without investigations demonstrating the absence of myocardial ischaemia
- Left ventricular ejection fraction measured at <30%
- Symptoms of decompensated heart failure syndrome in the last 3 months
- Severe obstructive lung disease
- Pregnancy at the time of enrolment or a desire to become pregnant during the study period
- Women who are breastfeeding
- Reduced life expectancy not associated with cardiovascular disease (less than 1 year)
- Unable to provide informed consent

Group 1 – Paroxysmal Atrial Fibrillation Group

- Any past history of episode of persistent atrial fibrillation at the time of enrolment to the study
- Treatment with any antiarrhythmic agent within six half-lives of that agent from before an administration of the study drug infusion

Group 2 – SVT Ablation Group

- Any past history of atrial fibrillation documented on 12 lead ECG or ambulatory ECG monitor
- Any past history of atrial flutter documented on 12 lead ECG or ambulatory ECG monitor
- Characterisation of SVT as any arrhythmia other than ANRT or AVNRT
- Treatment with any antiarrhythmic agent within six half-lives of that agent from the ablation procedure (including intra-procedural use) with the exception of isoprenaline and adenosine

Group 3 – Atrial Flutter Ablation Group

- Characterisation of arrhythmia as any arrhythmia other than cavo-tricuspid isthmus dependent atrial flutter at the time of ablation
- Treatment with any antiarrhythmic agent within six half-lives of that agent from the ablation procedure (including intra-procedural use) with the exception of isoprenaline and adenosine

Group 4 – Pulmonary Vein Isolation Group

- Requirement for a more extensive ablation strategy than pulmonary vein isolation alone
- Intra-procedural treatment with any antiarrhythmic agent with the exception of isoprenaline and adenosine
- Treatment with any antiarrhythmic agent in the days before the ablation within six half-lives of that agent from the ablation procedure

Participant Information

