If arrhythmia persists for greater than 10 minutes, it will be at the discretion of the attending clinician to decide whether to perform DC cardioversion, continue to wait or to proceed with the intended ablation procedure. If the participant is in persistent arrhythmia at the time of the start of the preablation infusion (most likely to occur in the atrial flutter ablation group) then that infusion will not be performed and the operator will proceed to the ablation procedure. Such participants will receive the post-ablation infusion as per protocol.

After the pre-ablation study drug infusion, the attending clinician will then proceed to the clinically indicated ablation procedure. The diagnosis and endpoint for the ablation procedure will be
recorded. When the attending physician is confident they have achieved their endpoint for the procedure, efforts will be made to induce a similar level of sedation as that recorded at the time of the pre-ablation study drug infusion. It is accepted that this may not be possible in the real world setting.

Once efforts have been made to achieve a similar level of sedation, the post-ablation study drug infusion will be administered using the standard infusion protocol for the identical infusion delivered prior to ablation.

All patients will be expected to leave the cardiac electrophysiology laboratory with a heart rate approaching that seen at baseline (if in sinus rhythm at the start of the procedure) and in sinus rhythm. It is accepted that some patients will require DC cardioversion if atrial fibrillation occurring during the infusion protocol persists for greater than 10 minutes.

It is also anticipated that it may be difficult for participants to tell whether they are undergoing a part of the study protocol or a part of their NHS ablation procedure at any particular time once they have entered the Cardiac Electrophysiology Laboratory. This is due to the use of sedation and the similarity between the participant experience in each part of the procedure. The potential for confusion will be clearly explained in the patient information sheet.

• Part B - Visit 3 – 6 week follow up

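### Clinical isoprenaline is allowed during the ablation in both arms, and the post-ablation study infusion starts with no isoprenaline-free interval or return-to-baseline condition

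*Protocol*

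**What the plan says.** **Exemption.** Under Exclusion Criteria, Groups 2 (SVT) and 3 (atrial flutter) may not have an antiarrhythmic agent within six half-lives of the ablation, "including intra-procedural use) with the exception of isoprenaline and adenosine". For Group 4 (pulmonary vein isolation) the matching line reads "Intra-procedural treatment with any antiarrhythmic agent with the exception of isoprenaline and adenosine". Neither line is limited by randomised arm or by time before a study infusion.

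**Expected use.** The Investigational Medicinal Product section says of isoprenaline in the electrophysiology laboratory: "It is considered a standard part of the procedure and is used in combination with programmed electronic stimulation to induce arrhythmias".

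**Which infusion is analysed.** Experiment 3 asks: "Does an infusion of the drug Isoprenaline induce Atrial Fibrillation in subjects following an ablation procedure for common type atrial flutter". Experiment 4 asks the same for the two SVT types ("Does an infusion of the drug Isoprenaline induce Atrial Fibrillation in subjects following an ablation procedure for either" AVRT or AVNRT). Both therefore rest on the infusion given after the ablation. Experiments 5 and 6 compare the infusions before and after it.

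**Start condition.** Part B, Visit 2: "Once efforts have been made to achieve a similar level of sedation, the post-ablation study drug infusion will be administered". The one heart-rate expectation in that section concerns leaving the laboratory, not starting the infusion.

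**Related rules.** Concomitant Drug Therapy restricts only epinephrine and potent inhalational anaesthetics. The list in Infusion Protocol of data recorded at all infusions covers sedation in the preceding 20 minutes but has no item for non-study isoprenaline or adenosine.

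**The concern.** The trial's stated reason for existing is that earlier isoprenaline work lacked a clean control. In Experiments 3 and 4 the control infusion comes straight after a procedure in which the protocol allows the test drug itself. If residual clinical isoprenaline contributes to atrial fibrillation during a placebo infusion, that event counts as placebo inducibility and the contrast shrinks.

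In Experiments 5 and 6 only the second infusion can be preceded by intra-procedural drug, because the first is given before catheters enter the heart. Any residual effect would then be indistinguishable from a change caused by the ablation.

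The placebo rate matters for two further reasons. The sample size assumes an almost event-free placebo arm. The Statistical analysis section also makes one-sided testing acceptable only if the placebo rate in the SVT or flutter group is zero, so a single carry-over event would change which test is allowed.

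**Working it through.** **1. Does any section close the gap?** Following Part B, Visit 2 in order:

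- The pre-ablation infusion is given before catheters enter the heart, so intra-procedural drug cannot precede it.
- The ablation follows, with isoprenaline exempt from the drug exclusion.
- The endpoint is reached and efforts are made to match sedation.
- The post-ablation infusion is then given.

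No interval or heart-rate condition stands between the last two steps. The only washout in Infusion Protocol is the 10 minutes of monitoring after a study infusion stops. A site could follow every rule and still give a placebo infusion soon after clinical isoprenaline.

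**2. The plan's own figure.** Experiment 3 states 31 per group for 90% power and aims for 35. Sample Size Calculation gives 31 for the pulmonary vein isolation group with 30% v 1%, chi-squared test, two-sided 5%. With pooled variance:

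n = [1.960 × √(2 p̄(1 − p̄)) + 1.282 × √(p₁(1 − p₁) + p₂(1 − p₂))]² / (p₁ − p₂)²

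With p₁ = 0.30, p₂ = 0.01 and p̄ = 0.155:

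- first term: 1.960 × √0.26195 = 1.003
- second term: 1.282 × √0.2199 = 0.601
- n = 1.604² / 0.0841 = 30.6, so 31 per group.

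The figure reproduces. At the 5% bound that Experiment 3 quotes for placebo, the same formula gives 47. The 31 therefore depends on a placebo rate near 1%.

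**3. Illustration for Experiment 3.** Inputs from the protocol: 35 per arm, 30% on isoprenaline, two-sided 5%, and Fisher's exact test (named for small numbers). Assumptions, because the protocol gives no rates: a share c of placebo participants has recent clinical isoprenaline, and a fraction r of those has extra atrial fibrillation because of it. The isoprenaline arm is held at 30%.

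Placebo rate = 0.01 + c × r × 0.99

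| c | r | Placebo rate | Exact Fisher power |
|---|---|---|---|
| 0 | – | 1% | 93.5% |
| 25% | 5% | 0.01 + 0.0124 = 2.2% | 88.5% |
| 50% | 5% | 0.01 + 0.0248 = 3.5% | 82.2% |
| 50% | 10% | 0.01 + 0.0495 = 6.0% | 68.3% |

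Power is evaluated at the rounded placebo rates.

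**4. Experiment 4.** The protocol calls it descriptive and says it cannot be powered properly (133 per group projected, 35 aimed for). At 10% v 1% with 35 per arm, Fisher power is about 10% even with no contamination, so no power loss is claimed there. The direction of bias in the estimate is the same.

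**The case against.** **Short action.** The protocol calls the duration of action brief, says side effects stop within moments of ending the infusion, and relies on this in its risk discussion. Re-matching sedation also takes some time. This stands: only recent dosing matters. But no half-life is given and no elapsed time is guaranteed.

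**Type of use.** The text on routine use describes induction to diagnose and categorise arrhythmias, which points to early in the procedure and fits the SVT group best. Group 3's endpoint is isthmus block, and nothing says isoprenaline is used to test it. So the evidence for exposure is strongest where the experiment is only descriptive. This stands, and it keeps the Experiment 3 power figures as illustration only.

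**Traceability.** Heart rate and blood pressure are recorded every minute during each infusion, and medical notes are source data. Exposure might therefore be recovered, although no specified item captures it.

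**Stronger readings that the protocol does not support.**

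- A reader might infer that the placebo arm does carry isoprenaline. The text shows only that it can.
- A reader might take the two-week rule (no participation where "study drug infusions for different parts of the study will occur closer than 2 weeks apart") as proof of long carry-over. It separates parts of the study, and for the same interval in Part A the stated reason is return to baseline medication and symptoms.
- The 10-minute washout is monitoring after a study infusion. It does not measure carry-over from clinical dosing.
- Adenosine is a co-exposure, not the test drug.
- The bias in Experiments 3 and 4 runs towards no effect, so it would not produce a false claim of induction.

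**Conclusion.** The gap is real. The protocol permits the test drug during the ablation in both arms, sets no interval or baseline condition before the post-ablation infusion, and does not list the exposure among the recorded data. Possible carry-over would pull Experiments 3 and 4 towards no difference and would be confounded with the ablation effect in Experiments 5 and 6.

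The size is unknown. Under the stated assumptions, power for Experiment 3 falls from 94% to between 89% and 68%. These figures depend wholly on assumed exposure and carry-over rates and on holding the isoprenaline arm at 30%. If clinical isoprenaline is rarely given late in the procedure, the effect is negligible.

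Should-fix: prevention is cheap, and exact timing may not be recoverable later if it is not recorded.

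**What to change.** 1. Reconcile Exclusion Criteria with Part B, Visit 2. State in the latter a minimum interval since the last non-study isoprenaline, or a return-to-baseline heart-rate condition, before the post-ablation study infusion. The investigators set the value, and it applies identically in both arms.
2. Add dose and start and stop times of non-study isoprenaline, and of adenosine as a co-exposure, to the data recorded at all infusions.
3. Report Experiments 3 to 6 also without participants in whom the condition was not met, as a sensitivity analysis.

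Cost: protocol wording, a few case report form fields, and a few minutes of laboratory time for participants who had clinical isoprenaline.

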The Participant Information Sheet (PiS) will be specific to the part of the study a subject is being recruited to. The "Participant Information Sheet for those being recruited to the Cardiac Ward based Infusion Protocol" will be for those recruited to protocol Part A and includes subjects in group 1. The "Participant Information Sheet for those being recruited to the Cardiac Electrophysiology Laboratory Infusion Protocol" will be for those recruited to protocol Part B and includes those from groups 2, 3 and 4. The "Additional Information Sheet for those undergoing an ablation for Atrial Flutter or Atrial Fibrillation" will be given to participants recruited to groups 3 and 4.

Informed Consent

Informed consent to enter the study must be sought from each participant. This will be taken only after a full explanation has been given, an information leaflet offered and time allowed for consideration. Signed participant consent will be obtained. The right of the participant to refuse to participate without giving reasons will be respected.

Sample Size Calculation

The sample size calculation for estimation of the proportion of disagreement between repeated isoprenaline infusions in terms of ability to induce atrial fibrillation is based on the width of a 1-sided 95% confidence interval (CI). Assuming that the proportion of disagreement will be \leq 10%, a sample size of 35 patients would enable the proportion to be estimated with an upper limit of the 1-sided 95%CI for the proportion of \leq 20%.

A 1-sided CI is used as we only wish to ensure that the upper limit of the estimated proportion of disagreement is less than a given cut-off (20% has been chosen to indicate clinically significant disagreement); the lower limit of the CI is immaterial as the lower the proportion of disagreement the better, so we do not need to restrict this.

The sample size calculation for the randomised comparison of proportion of participants inducible in the placebo and isoprenaline arms is based on the chi-squared test. In the Pulmonary Vein Isolation Group, assuming that almost no participants in the placebo arm will be inducible (1%), and that the proportion of participants in the active drug (isoprenaline) arm who are inducible will be 30%, then 31 patients in each arm will be required for 90% power (assuming 2-sided significance of 5%).

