It is noted that previous literature suggests that the proportion of patients with a past history of atrial fibrillation who are inducible with isoprenaline is greater than 80%. This does not fit with our interpretation of day to day clinical practice and hence the study is powered to detect a far lower arte of inducibility. We will however perform a pre-specified interim analysis of the Pulmonary Vein Isolation Group once 10 participants with a past history of atrial fibrillation have been randomised to each arm of the study (Experiment 2). If a significant result is detected, enrolment to that block will be discontinued.

Statistical analysis

The analysis of the disagreement between repeated isoprenaline infusions in terms of ability to induce atrial fibrillation will estimate the proportion of disagreement with a 1-sided 95%CI for the proportion. A 2-sided 90%CI is first calculated and the upper limit of this interval gives the required upper limit of a 1-sided 95%CI. If the estimated upper limit is < 20% (the chosen cut-off for clinically significant disagreement) then agreement between repeated infusions will be considered acceptable.

The randomised comparison of proportion of patients inducible between placebo and isoprenaline will use the chi-squared test or the Fisher's exact test if numbers of patients in some categories are small.

It is anticipated that the rate of induced episodes of arrhythmia in a number of the groups where they are being given placebo infusion will approach zero. If the results of the study demonstrate that the rate of inducibility in the SVT group or atrial flutter group being given placebo infusion is zero, we would consider it acceptable to use one sided tests of significance.

Study Duration

We aim to recruit 235 participants over a 24 month recruitment period. It is anticipated that the majority of subjects will be recruited from the Bournemouth site.

- Start Date: 01/09/2014
- Estimated Date of End of Trial: 01/09/2017
- Maximum Duration of Participation: 12 months

Study Procedure

The study will require a minimum of 2 encounters with the study team. For subjects in the group of participants requiring the most visits, the study schedule requires 7 visits over 12 months. Usual care for this group would involve 4 visits to hospital, one of these is not required by the study participants and 3 are combined with study visits.

Infusion Protocol

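### Experiment 2's 90% power is computed for the uncorrected chi-squared test, but under the protocol's own switch to Fisher's exact test it is about 86–87% at 30 per group and 88–89% at 31

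*Protocol*

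**What the plan says.** Protocol, Sample Size Calculation: the number needed to compare the proportions "inducible in the placebo and isoprenaline arms is based on the chi-squared test". The inputs are 1% inducible on placebo and 30% on isoprenaline in the Pulmonary Vein Isolation Group. With 90% power and two-sided 5% significance, they give 31 per arm.

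Protocol, Study Objectives, Experiment 2: the same 31 is printed, followed by two scenarios for higher event rates, "15 participants per group for event rate >50%, 6 participants per group for event rate >80" (per cent). The target is then set: "Aim to recruit 30 participants per group".

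Protocol, Statistical analysis: the comparison "will use the chi-squared test or the Fisher's exact test if numbers of patients in some categories are small". What counts as small is not defined. The same section expects placebo rates in a number of groups to come close to zero. It allows one-sided tests only in the SVT and atrial flutter groups, so Experiment 2 stays two-sided. The Sample Size Calculation section adds an interim look at Experiment 2 with 10 per arm, which stops enrolment on a significant result. It states no adjusted level.

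**The concern.** The power figure and the analysis rule refer to different tests. With a placebo rate of 1%, 30 placebo patients yield 0.3 expected events, so the sparse-table clause is likely to be used. Fisher's test is conservative in such tables: at 30 per arm its true two-sided level never exceeds 2.7%. Results near the boundary, such as 0 v 5 or 1 v 7 events, are significant on chi-squared (p = 0.020 and 0.023) but not on Fisher (p = 0.052 for both). Their smallest expected counts are 2.5 and 4, so the usual reading of the rule sends them to Fisher. A reader relying on the printed 90% would therefore overestimate the chance that Experiment 2 succeeds at its design rates.

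**Working it through.** **Inputs.** Placebo 1%, isoprenaline 30%, two-sided 5%, 90% power, 31 per arm (Sample Size Calculation). Target 30 per group; scenarios of 15 per group at 50% and 6 per group at 80% (Experiment 2). Target 35 per group (Experiment 3). Allocation 1:1 (Study Procedure, Protocol Part B).

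**Step 1: reproduce the printed sizes.** Uncorrected chi-squared formula, with p̄ the mean of the two rates:

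n = [1.960·√(2p̄(1−p̄)) + 1.282·√(p₁(1−p₁) + p₂(1−p₂))]² / (p₂−p₁)²

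For 1% v 30%, p̄ = 0.155, so n = [1.960·√0.26195 + 1.282·√0.2199]² / 0.29² = 30.6, which rounds up to 31. The same formula gives 14.4 → 15 at 50% and 5.7 → 6 at 80%. All three printed figures are reproduced. With a continuity correction they would be 38, 19 and 9, so the printed sizes are the uncorrected ones.

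**Step 2: how often the rule selects Fisher.** At 30 per group the smallest expected cell count at the design rates is 30 × (0.01 + 0.30)/2 = 4.65. Applying expected count below 5 to each realised table, Fisher is used in 54% of trials at 30 per group and 49% at 31. If small refers to observed counts below 5, Fisher is used almost always.

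**Step 3: power under Fisher at 30 per group.** The smallest significant results are 0 v 6, 1 v 8 and 2 v 9. Summing the binomial probabilities:

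- 0 placebo events: 0.740 × P(at least 6 of 30) = 0.740 × 0.923 = 0.683
- 1 placebo event: 0.224 × P(at least 8 of 30) = 0.224 × 0.719 = 0.161
- 2 placebo events: 0.033 × P(at least 9 of 30) = 0.033 × 0.569 = 0.019
- 3 or more: about 0.001

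The total is 0.864.

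**Step 4: power under Fisher at 6 per group, 1% v 80%.** With no placebo event, 0 v 4 fails (p = 0.061) and 0 v 5 succeeds (p = 0.015). With one placebo event, 6 of 6 is needed. Power = 0.99⁶ × 0.655 + 6(0.01)(0.99⁵) × 0.262 = 0.617 + 0.015 = 0.632.

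**Step 5: all cases, by full enumeration.** The rule column uses chi-squared when all expected counts are at least 5.

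| Per group | Rates | Chi-squared formula | Fisher | Rule |
|---|---|---|---|---|
| 30 | 1% v 30% | 89.4% | 86.4% | 86.9% |
| 31 | 1% v 30% | 90.4% | 88.2% | about 89% |
| 35 | 1% v 30% | 93.6% | 93.5% | 94.1% |
| 15 | 1% v 50% | 91.2% | 90.3% | 90.5% |
| 6 | 1% v 80% | 91.8% | 63.2% | 63.2% |

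Fisher reaches 90% at 33 per group for 1% v 30% (91.2%; 32 gives 89.8%) and at 8 per group for 1% v 80% (93.2%; 7 gives 83.3%).

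**Step 6: the alternative test.** For a single look at 30 per group, Boschloo's unconditional exact test has 92.6% power and a maximum size of 4.7%. With looks at 10 and 30 per arm, both at 0.05, the maximum overall type I error is 7.9% for Boschloo and 3.7% for Fisher, in each case at a common rate of 0.5.

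**The case against.** Fisher's test for sparse tables is conventional and valid, and details of the test are often left to a statistical analysis plan, which is not at hand. At the printed 31 per arm Fisher gives 88.2%, within 2 points of 90%; a 30% isoprenaline rate is itself a guess, and the gap is small beside that uncertainty. Fisher's conservatism also does useful work here, because it keeps the unadjusted two-look design below 5%. All of this stands and limits the weight of the point. What remains is that the protocol itself prints the sizing test, the analysis rule, the sizes and the power, and these do not fit together for Experiment 2.

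Four stronger readings are tempting, and the protocol does not support them:

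- That all the randomised comparisons are underpowered. Experiment 3 aims for 35 per group, where Fisher gives 93.5% at 1% v 30%. Experiment 4 is declared descriptive and makes no power claim.
- That an analysis will be run with 63% power. Six per group is a printed illustration. The smallest planned analysis is the interim at 10 per arm, where Fisher power at 1% v 80% is 98.2%.
- That the whole gap at 30 per group is due to the test. Under Fisher, going from 31 to 30 costs 88.2 − 86.4 = 1.8 points, half of the 90 − 86.4 = 3.6.
- That the plan will mostly not use chi-squared. On the expected-count reading the split is close to even.

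**Conclusion.** The point holds for Experiment 2 only, and it is modest. At the protocol's own 1% v 30%, the written rule gives 86–87% power at the 30 per group aimed for and 88–89% at 31, against a stated 90%. The 6-per-group scenario falls further, to 63%, and should read 8; the 15-per-group scenario holds at 90.3%.

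These figures assume a single final analysis, two-sided 5%, and a 1% placebo rate accepted in full. The Experiment 2 entry puts the placebo rate only below 5%. At 5% v 30%, Fisher power at 30 per group would be 63.1%. That is a larger loss, but it concerns the assumed rate and is separate from the choice of test.

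**What to change.** In Study Objectives (Experiment 2) and Sample Size Calculation, restate Experiment 2's power for the test that will be used: under Fisher, about 86% at 30 per group and 88% at 31. Change 6 per group at 80% to 8. In Statistical analysis, say what counts as small. This takes a few sentences and no extra patients. If 90% under Fisher is wanted, 33 per group is needed, 3 more per arm than the current target.

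Alternatively, prespecify one unconditional exact test, such as Boschloo's, for Experiment 2. That gives 92.6% at 30 per group for a single look with no added recruitment. It should be adopted only with an adjusted significance level for the interim look at 10 per arm, and the power recalculated at that level. The 6-per-group figure would still need restating, since Boschloo gives 88.6% there. Experiments 3 and 4 need no change on this account.
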